**RESEARCH PROTOCOL**Document Code:
EY. FR. 16

Revision Date: 24.03.2023

Revision No: 03

Version No: 01

Page No: 1 / 5

Date: 07/03/2023**1. RESEARCH TITLE:****Effect of kinesiology tape on pain, posture, balance and respiration in ankylosing spondylitis: a randomized controlled trial****2. RATIONALE AND JUSTIFICATION OF THE RESEARCH:**

Ankylosing Spondylitis (AS) is a chronic inflammatory disease characterized by inflammation, especially in the enthesis regions and surrounding bone tissue of the spine.

- Fusion in adjacent vertebral segments in AS leads to reduced axial movement and mechanical stiffness(1).
- Secondary to spinal deformities such as decreased lumbar lordosis, increased thoracic kyphosis, and loss of cervical lordosis, patients with AS may develop hip flexion contracture, resulting in compensatory knee flexion(2).
- The increase in spinal kyphosis causes the center of gravity to shift forward and downward. It is suggested that hip and knee flexion, along with plantar flexion, occur to compensate for this shift and keep the center of gravity within the base of support(3).
- Furthermore, due to increased spinal kyphosis, patients find it difficult to look forward, leading to limitations in daily living activities such as driving, personal care, and social communication(4).
- Pulmonary involvement in AS is typically asymptomatic and includes anomalies of the thoracic cage and lung parenchyma. Reduced lung volumes are one of the most important findings of this disease.

Chest wall rigidity in these patients is caused by bony ankylosis in the sternomanubrial, sternoclavicular, costovertebral joints, and thoracic vertebrae. Progressive chest wall deformities, such as kyphosis, are subsequently added to this clinical picture. In later stages of the disease, all these involvements result in reduced chest wall movement and increased respiratory problems(7).

RESEARCH PROTOCOL

Document Code:
EY. FR. 16

Revision Date: 24.03.2023

Revision No: 03

Version No: 01

Page No: 2 / 5

- Non-pharmacological approaches, such as education, exercise, and physical therapy, are considered important cornerstones of AS treatment, alongside pharmacological treatments.
- Kinesio Tape (KT) lifts the skin, increasing the area of the skin and subcutaneous tissue, thereby enhancing circulation and movement. Consequently, it reduces inflammation in the area and accelerates circulation and tissue healing.
- The second mechanism involves stimulating mechanical receptors on the skin, sending impulses to the central nervous system via tactile stimulation. It has been reported that the resulting impulse provides stimulation/inhibition and neuromuscular re-education(5).
- Moreover, it is argued that the activated gate control mechanism due to these sensory stimuli, along with the release of fascia through space enlargement, increased circulation, and mechanical support, reduces pain(6).

In light of all this information, it is hypothesized that a non-pharmacological approach using a home exercise program (HEP) (spinal extensor strengthening, posture, and balance exercises) and the Kinesio Taping technique in AS patients may achieve reduced pain symptoms, correction of postural deformities, and an increase in respiratory capacity.

REFERENCES

4. Uçkun A, Sezer İ. Ankilozan spondilit ve denge. *Eurasian Journal of Medicine*. 2017;49(3):207-10

RESEARCH PROTOCOL

Document Code:
EY. FR. 16

Revision Date: 24.03.2023

Revision No: 03

Version No: 01

Page No: 3 / 5

3. OBJECTIVE OF THE RESEARCH:

The aim of this study is to investigate the effect of Kinesio Taping on pain, posture, balance, and respiration in ankylosing spondylitis and to demonstrate the difference between this technique and routine home exercises provided to this group of patients.

4. EXPECTED BENEFITS OF THE RESEARCH:

Investigation of the efficacy of the KT method on pain, posture, balance, and respiration in AS patients.

5. RESEARCH METHODOLOGY:

Participants:

Eighty patients aged 18–65, diagnosed with ankylosing spondylitis, not in the acute flare period, who applied to the Physical Medicine and Rehabilitation (PMR) outpatient clinic of Bursa Yuksek Ihtisas Training and Research Hospital between April 1, 2023, and January 1, 2024, will be included in the study.

- Inclusion Criteria: Patients over 18 years old diagnosed with ankylosing spondylitis
- Exclusion Criteria: Patients with active malignancy, active cellulitis and skin infection, open wounds, deep vein thrombosis, and patients with vestibular and orthopedic pathologies affecting balance.

Intervention:

- Group 2: Will receive only a home exercise program (HEP: spinal extensor strengthening, posture, balance, and respiratory exercises) for 5 weeks, 5 days a week, 3 sets of 10 repetitions.
- Group 1: Will receive the home exercise program in addition to Kinesio Taping applied by a physician to

BURSA YUKSEK İHTİSAS TRAINING AND RESEARCH HOSPITAL

RESEARCH PROTOCOL

Document Code:
EY. FR. 16

Revision Date: 24.03.2023

Revision No: 03

Version No: 01

Page No: 4 / 5

the thoracic, lumbar, and cervical regions in the hospital setting. The KT will remain on the patient for 5 days and then be removed by the patient. The tape will be applied once a week for 5 weeks.

Outcome Measures:

At the end of the 5 weeks, the following will be used for patient assessment: VAS, Range of Motion (ROM), BASMI, BASFI, BASDAI, fingertip-to-floor distance, modified Schober test, chest expansion, AS quality of life questionnaire, and Berg Balance Scale.

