6. DATA COLLECTION TOOLS

- Information-Questionnaire Form
- Self-administered Questionnaire
- Questionnaire administered under observation
- Interviewer-administered Questionnaire
- Observation
- Laboratory examination
- Record from archives
- Other (Specify): ROM measurement with a goniometer will be conducted in the outpatient clinic setting. Fingertip-to-floor distance, chest expansion, and modified Schober measurement will be taken with a tape measure.

NOTE: Please also submit a detailed list of where the required information/laboratory tests will be obtained, along with the pre-authorization letters from the clinics and laboratories.

7. STATISTICAL METHODS FOR DATA ANALYSIS:

- Data analysis will be performed using the IBM SPSS 22.0 statistical software package.
- In addition to descriptive statistical methods (frequency, percentage, mean, standard deviation, median, min-max), the Chi-Square (χ²) test will be used for comparing qualitative data.
- The suitability of the data for normal distribution will be evaluated using the Kolmogorov-Smirnov and Shapiro-Wilk tests.

T.C. Sağlık Bakanlığı
Türkiye Kamu
Hastaneleri Kurumu

BURSA YUKSEK İHTİSAS TRAINING AND RESEARCH HOSPITAL

RESEARCH PROTOCOL

Document Code:
EY. FR. 16

Revision Date: 24.03.2023

Revision No: 03

Version No: 01

Page No: 5 / 5

- If correlation analysis is performed, the Spearman test will be used when the data does not show normal distribution, and the Pearson test will be used when it does.
- For intergroup analysis, the Independent T-test will be applied if normal distribution is detected, and the Kruskal-Wallis test will be applied if abnormal distribution is detected.
- Probability values (P) less than 0.05 will be accepted as significant, indicating a difference between the groups, while values greater than 0.05 will be considered non-significant, indicating no difference between the groups.

8. PLANNED DURATION OF THE RESEARCH:

- Planned Start Date: 01/05/2023
- Planned End Date: 01/01/2024

9. CONTACT PERSON FOR THE RESEARCH:

- Name Surname: [name]
- [contact]
- Date: 07/03/2023

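### Does a planned end on the day recruitment closes leave late starters without their week-5 assessment?

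*Combined protocol and SAP*

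**What the plan says.** Section 5 (Participants) sets a target of 80 patients and defines the window by when they came to the clinic: those "who applied to the Physical Medicine and Rehabilitation (PMR) outpatient clinic" of the hospital "between April 1, 2023, and January 1, 2024, will be included in the study".

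Section 5 (Intervention) gives both groups the same duration. The home exercise programme runs "for 5 weeks, 5 days a week, 3 sets of 10 repetitions". In Group 1, "The tape will be applied once a week for 5 weeks", and for each application "The KT will remain on the patient for 5 days and then be removed by the patient".

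Section 5 (Outcome Measures) fixes a single assessment time: "At the end of the 5 weeks, the following will be used for patient assessment".

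Section 8 (Planned duration of the research) consists of two dates, "Planned Start Date: 01/05/2023" and "Planned End Date: 01/01/2024". It does not say whether the second marks the end of recruitment, the last assessment or the close of the project. No section names a last-enrolment date or a last-assessment date.

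**The concern.** The last day on which a patient may present and the last day of the research are the same, yet every patient needs five more weeks to reach the only assessment that the plan describes. If Section 8 is taken to cover follow-up, the two sections cannot both hold for a patient who starts late in the window.

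The stake would be completeness of the outcome data. All the listed measures are taken at week 5, and Section 7 has no rule for missing values. A late starter might be assessed after the planned end, be assessed early, or not be assessed at all, and Section 8 does not say which. The opening dates differ too: the window in Section 5 opens on 1 April 2023, while Section 8 starts the study on 1 May 2023.

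**Working it through.** The plan states no last-start date or accrual rate, so there is no figure of its own to reproduce. The check is calendar arithmetic on the stated dates.

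**Inputs**

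| Input | Value | Source |
|---|---|---|
| Window for presenting to the clinic | 1 April 2023 to 1 January 2024 | Section 5, Participants |
| Planned start | 1 May 2023, read day-first as in the form's revision date 24.03.2023 | Section 8 |
| Planned end | 1 January 2024 (same in either date order) | Section 8 |
| Intervention, then assessment | 5 weeks = 35 days | Section 5, Intervention and Outcome Measures |
| Sample size | 80 | Section 5, Participants |

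**Latest start with week 5 inside the planned end**

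- Planned end minus 35 days: 1 January 2024 − 35 = 27 November 2023.
- A start on 28 November is assessed on 2 January 2024, one day after the planned end.
- A start on 1 January 2024 is assessed on 5 February 2024.
- Sensitivity: with the first tape on day 0, the fifth goes on at day 28 and comes off at day 28 + 5 = 33. Taking day 33 as the end of treatment gives 29 November. Counting days inclusively (34 days) gives 28 November. The cut-off moves by at most two days.

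**How many patients could start late**

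The documents do not determine this. As an illustration, assume even accrual to the last day and treatment starting on the day of presentation. The expected number is then 80 × (days after the cut-off ÷ days in the window):

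- From 1 April (275 days): 35/275 = 12.7%, and 80 × 0.127 = 10.2 patients.
- From 1 May (245 days): 35/245 = 14.3%, and 80 × 0.143 = 11.4 patients.
- With the 33-day version: 80 × 33/275 = 9.6 and 80 × 33/245 = 10.8 patients.

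Faster early accrual lowers these figures, to zero if all 80 have started by 27 November. Slow early accrual, or a delay between presentation and first treatment, raises them.

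**Accrual needed for nobody to be late**

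| Opening date | 80 patients by 1 January | 80 patients by 27 November |
|---|---|---|
| 1 April | 275/7 = 39.3 weeks; 2.04 per week | 240/7 = 34.3 weeks; 2.33 per week |
| 1 May | 245/7 = 35 weeks; 2.29 per week | 210/7 = 30 weeks; 2.67 per week |

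With the opening date held fixed, finishing by 27 November needs about 0.3 (from 1 April) or 0.4 (from 1 May) more patients per week.

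**What depends on the end date**

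The between-group comparisons in Section 7 are an independent t-test or a rank-based alternative, and a chi-square test for qualitative data. None uses calendar time. The sample size is a fixed count, not a number of events or a length of observation. No interim look or stopping rule refers to the date. Moving the end by five weeks changes no input to the analysis.

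**The opening dates**

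Section 5 dates presentation to the clinic, so a patient can present in April and begin in May. No outcome is lost.

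**The case for a change.** The strongest case for a change is that Section 8 is the only statement of study length, that its heading refers to the research and not to recruitment, and that nothing elsewhere lets assessment run past it. Week 5 is the only assessment time given, so a patient cut off by the end date would have no planned outcome and no missing-data rule to fall back on. A delay between presentation and treatment only lengthens the overrun. Correcting the dates would take one line.

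Much of this stands. The dates are current text, the subtraction is exact, and the sections do not fit together if the end date includes follow-up. What does not stand is the step from there to lost outcomes. The end date is undefined, and because it coincides with the close of the window in Section 5 it may simply mark the end of recruitment. On either reading, the only instruction about when to assess a patient is the one in Section 5, and it is relative to that patient's treatment. No text tells the investigator to assess early or to stop collecting data on 1 January 2024. The window also sets outer limits for a fixed 80 patients, and recruitment can stop once that number is reached.

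**Conclusion.** The dates in Sections 5 and 8 are loosely matched, and the gap is one that study staff fill sensibly. A patient who starts in December is assessed five weeks later, as Section 5 requires, and the project closes a few weeks after its nominal date: at the latest on 5 February 2024 if treatment begins on the day of presentation, and later by any lag.

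The number of patients concerned is unknown from the documents. It may be zero, and it is about 10 to 11 of 80 under the stated even-accrual assumption, which is not a bound. Even then, the cut-off is a calendar date that falls on both groups alike, so the documents give no reason to expect differential loss. No estimate, power statement or error rate depends on the end date. Stating separate dates for last start and last assessment would be tidy housekeeping, but it would alter no result or conclusion.

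This rests on two readings: that the timing in Section 5 governs when a patient is assessed, and that the planned end is a planning figure that may slip. An explicit statement that data collection closes on 1 January 2024 would reopen the point, but the documents contain none.

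### Ten outcomes, no primary and no success rule: the plan does not say which result decides whether taping works

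*Combined protocol and SAP*

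**What the plan says.** Section 5 (Outcome Measures) gives one time point, "At the end of the 5 weeks, the following will be used for patient assessment", followed by ten measures of equal standing: "VAS, Range of Motion (ROM), BASMI, BASFI, BASDAI, fingertip-to-floor distance, modified Schober test, chest expansion, AS quality of life questionnaire, and Berg Balance Scale". None is called primary or secondary anywhere in the document.

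Section 3 sets the aim: to "investigate the effect of Kinesio Taping on pain, posture, balance, and respiration in ankylosing spondylitis". That is four domains, unranked and not tied to measures. The hypothesis at the end of Section 2 is that home exercise together with taping "may achieve reduced pain symptoms, correction of postural deformities, and an increase in respiratory capacity". That is three domains; balance is not among the expected effects.

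Section 7 gives one rule for quantitative comparisons between groups: "For intergroup analysis, the Independent T-test will be applied if normal distribution is detected", with Kruskal-Wallis otherwise (chi-square is for qualitative data). It then states: "Probability values (P) less than 0.05 will be accepted as significant, indicating a difference between the groups". It contains no ordering of outcomes, multiplicity adjustment, composite or rule for overall success. It does not say whether tests are one- or two-sided.

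**The concern.** The trial is meant to show whether taping adds something to home exercise. Suppose chest expansion gives P = 0.03 and VAS gives P = 0.40. Nothing in the plan says whether the trial was positive. That gap needs no assumption about error rates or correlations.

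The error rate is a further issue. Nothing in the plan prevents an overall claim for taping from resting on whichever of the ten outcomes happens to cross 0.05, and the 5% rate does not apply to a claim chosen that way. A primary outcome named after the results are known would not repair this, because it could be the one that crossed the line by chance.

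**Working it through.** The plan states no power, sample-size derivation or overall error rate, so there is no figure of its own to reproduce.

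**Inputs**
- Number of tests m = 10 (Section 5). ROM is one entry, but Section 6 does not say how many goniometer readings it yields, so ten is a minimum.
- Level per test 0.05 (Section 7). Two-sided testing is assumed because Section 7 defines significance as "indicating a difference between the groups"; this gives 0.025 per test in the direction of benefit.
- Correlation ρ between outcomes: not in the documents. Common values from 0 to 0.9 are assumed.
- Condition: tape has no effect, and any one significant result is taken as success.

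**Independence (ρ = 0)**
- Either direction: 1 − 0.95^10 = 0.401.
- Apparent benefit: 1 − 0.975^10 = 0.224.

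**Common correlation ρ.** With Φ and φ the normal distribution and density functions, the chance of at least one apparent benefit is

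1 − ∫ Φ((1.96 − √ρ·x)/√(1−ρ))^m φ(x) dx.

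For either direction, Φ((−1.96 − √ρ·x)/√(1−ρ)) is subtracted inside the power.

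| ρ | Benefit, m = 10 | Either direction, m = 10 | Benefit, m = 4 | Either direction, m = 4 |
|---|---|---|---|---|
| 0 | 22.4% | 40.1% | 9.6% | 18.5% |
| 0.3 | 17.8% | 35.1% | 8.7% | 17.4% |
| 0.5 | 14.4% | 28.7% | 7.8% | 15.6% |
| 0.7 | 10.7% | 21.3% | 6.5% | 13.0% |
| 0.9 | 6.4% | 12.8% | 4.7% | 9.4% |

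The m = 4 columns assume one measure for each domain in the Section 3 aim, a mapping the plan does not make. Simulated t-tests with 40 per group (assumed; the plan gives only a total of 80) agree for m = 10: 40.2% and 22.5% at ρ = 0, and 21.5% and 10.6% at ρ = 0.7.

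If ROM were analysed as, say, five readings (m = 14), the benefit figure would run from 29.8% at ρ = 0 to 7.0% at ρ = 0.9.

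**A single primary** gives 5% in either direction and 2.5% for apparent benefit. Section 7's rule of testing normality and then choosing a test does not disturb this: simulated type I error with 40 per group was 0.048, 0.052 and 0.047 for normal, lognormal and exponential data.

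**Gated Holm** (secondaries tested only if the primary is significant). Simulated familywise error was 0.050 at every ρ when all ten outcomes are null, and at most 0.049 when only the primary is effective.

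**The case against.** The strongest reply is that the plan never says one significant result out of ten proves that taping works. Section 7 interprets each P value separately, and read that way each test holds its 5% level. This stands. A reader might infer that the trial has a false-positive rate of 22% or 40%. The documents do not support that: those figures describe a decision rule the plan does not contain, and their upper ends require independent outcomes, which is unlikely for measurements on the same patients.

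The second reply is that ten chances overstates the matter, since the aim has four domains and the quality of life questionnaire is, by its name, in none of them. This also has weight. With one measure per domain the figures fall to about 5–10% and 9–19%. But the plan does not assign measures to domains, so this reduces the size without closing the gap.

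A third reply is that requiring all three parts of the Section 2 hypothesis would avoid inflation. Under such a rule the chance of false success would be about 1% or less at every correlation considered. However, the plan neither adopts the rule nor names the measures, and that hypothesis concerns exercise and taping together, not the added effect of tape over exercise.

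**Conclusion.** The plan lacks a primary outcome and any rule for overall success, and this must be fixed before data are examined. That conclusion can be read directly from Sections 3, 5 and 7 and rests on no assumption.

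The size is conditional. If any one of the ten outcomes were taken as success and tape did nothing, an apparent benefit would arise about 6–22% of the time and a difference in either direction about 13–40%. With four outcomes the ranges are about 5–10% and 9–19%. All assume two-sided tests and common correlations from 0.9 to 0; several ROM readings would raise them. It would go too far to say that the individual tests are invalid or that the plan defines success as any one significant result.

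**What to change.** In Section 5, before any data are examined, name one primary outcome, chosen by the sponsor, with its exact measure and the 5-week time point. Analyse the 5-week value. Use change only if a baseline measurement is confirmed, since the documents state none. If VAS is chosen, say what it measures. If ROM is the primary or is formally tested, name a single ROM measurement in advance.

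In Section 7, rest the confirmatory conclusion on the primary alone at two-sided 0.05. Label the other nine secondary, and either report them as estimates with 95% confidence intervals and no confirmatory claim, or test them by Holm's method only if the primary is significant.

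The cost is a few sentences, and no extra assessments if the 5-week value is used. The downside is that nine outcomes lose stand-alone significance. Under gated Holm the first threshold is 0.05/9 = 0.0056. With 40 per group and no dropout (assumed), a secondary effect of 0.83 SD has 80% power at that threshold taken alone; at 0.05, 0.63 SD is enough. If the primary itself has 80% power, the chance of passing both is about 64% / 67% / 69% / 71% at correlations 0 / 0.3 / 0.5 / 0.7. That is near a floor, because Holm's thresholds relax after each rejection: if all nine secondaries have that effect, the chance is about 75–77%.

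The documents give no basis for the sample size, so whether 80 patients suffice for the chosen primary still has to be checked.

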6. DATA COLLECTION TOOLS

- Information-Questionnaire Form
- Self-administered Questionnaire
- Questionnaire administered under observation
- Interviewer-administered Questionnaire
- Observation
- Laboratory examination
- Record from archives
- Other (Specify): ROM measurement with a goniometer will be conducted in the outpatient clinic setting. Fingertip-to-floor distance, chest expansion, and modified Schober measurement will be taken with a tape measure.

NOTE: Please also submit a detailed list of where the required information/laboratory tests will be obtained, along with the pre-authorization letters from the clinics and laboratories.

7. STATISTICAL METHODS FOR DATA ANALYSIS:

- Data analysis will be performed using the IBM SPSS 22.0 statistical software package.
- In addition to descriptive statistical methods (frequency, percentage, mean, standard deviation, median, min-max), the Chi-Square (χ²) test will be used for comparing qualitative data.
- The suitability of the data for normal distribution will be evaluated using the Kolmogorov-Smirnov and Shapiro-Wilk tests.

T.C. Sağlık Bakanlığı
Türkiye Kamu
Hastaneleri Kurumu

BURSA YUKSEK İHTİSAS TRAINING AND RESEARCH HOSPITAL

RESEARCH PROTOCOL

Document Code:
EY. FR. 16

Revision Date: 24.03.2023

Revision No: 03

Version No: 01

Page No: 5 / 5

- If correlation analysis is performed, the Spearman test will be used when the data does not show normal distribution, and the Pearson test will be used when it does.
- For intergroup analysis, the Independent T-test will be applied if normal distribution is detected, and the Kruskal-Wallis test will be applied if abnormal distribution is detected.
- Probability values (P) less than 0.05 will be accepted as significant, indicating a difference between the groups, while values greater than 0.05 will be considered non-significant, indicating no difference between the groups.

8. PLANNED DURATION OF THE RESEARCH:

- Planned Start Date: 01/05/2023
- Planned End Date: 01/01/2024

9. CONTACT PERSON FOR THE RESEARCH:

- Name Surname: [name]
- [contact]
- Date: 07/03/2023

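### No baseline assessment is stated and the quantity compared between groups is undefined; measuring baseline and adjusting for it would add precision at small cost

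*Combined protocol and SAP*

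**What the plan says.** Under Outcome Measures, section 5 introduces the ten outcomes with "At the end of the 5 weeks, the following will be used for patient assessment". The list runs from VAS to the "AS quality of life questionnaire, and Berg Balance Scale". No earlier assessment is mentioned there or elsewhere.

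For the group comparison, section 7 states "For intergroup analysis, the Independent T-test will be applied if normal distribution is detected". The alternative for data that fail the normality check is a rank test: "the Kruskal-Wallis test will be applied if abnormal distribution is detected". Section 7 also lists descriptive statistics, a chi-square test, normality tests and optional correlations. It contains no paired test, change score, covariate or ANCOVA, and does not say which quantity enters the t-test or Kruskal-Wallis test.

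Two other places bear on this. The hypothesis at the end of section 2 is worded as change: treatment "may achieve reduced pain symptoms, correction of postural deformities, and an increase in respiratory capacity". The objective in section 3 is a contrast between groups: "to demonstrate the difference between this technique and routine home exercises provided to this group of patients". Randomization appears only in the title, which calls the study "a randomized controlled trial".

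**The concern.** Three things are missing.

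- **The analysed quantity.** The same t-test can be run on week-5 values or on changes, and the two can differ a good deal in power. With ten outcomes and nothing fixed, the choice could be made after the data are seen. If changes are meant, a baseline must be measured, and none is stated.
- **A starting point for the hypothesis.** Reduction, correction and increase cannot be described without a value before treatment.
- **Precision.** Each outcome's own baseline value usually explains part of its week-5 variation. An unadjusted test, parametric or rank-based, leaves that variation in the error term. With 80 patients and no power basis in the plan, that may matter.

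**Working it through.** **Inputs from the documents.** Total of 80 patients and two groups (section 5); significance level 0.05 (section 7).

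**Assumptions not in the documents.** 1:1 allocation (n = 40 per arm), two-sided testing, an effect of d = 0.5 SD, equal SDs at baseline and week 5, normal data, no dropout, and baseline-to-week-5 correlation r = 0.3, 0.5 or 0.7. The plan gives no power calculation, so there is no figure of its own to reproduce.

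**Method.** Power comes from the noncentral t distribution with noncentrality d / √(2V/n). V is the variance relative to that of week-5 values. The 95% CI half-width is t × √(2V/n), with t ≈ 1.991.

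*Week-5 values.* V = 1, df = 78. Noncentrality = 0.5/√(2/40) = 0.5/0.2236 = 2.236. Power is 59.8% and the half-width is 0.445 SD.

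*ANCOVA.* V = (1 − r²)(1 + 1/76), df = 77. The second factor is the expected loss from chance imbalance in the covariate.

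*Change scores.* V = 2(1 − r), df = 78.

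| r | ANCOVA V | ANCOVA power | ANCOVA half-width | Change V | Change power |
|---|---|---|---|---|---|
| 0.3 | 0.922 | 63.3% | 0.428 SD | 1.4 | 46.3% |
| 0.5 | 0.760 | 71.7% | 0.388 SD | 1.0 | 59.8% |
| 0.7 | 0.517 | 86.7% | 0.320 SD | 0.6 | 81.4% |

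The ANCOVA gain over the week-5 t-test is 3.5, 11.9 and 26.9 points. An unadjusted t-test would need 44, 53 and 77 per arm for the same power. At r = 0, V = 1.013 and power is 59.2%, a loss of 59.8 − 59.2 = 0.6 points.

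Change scores have less power than week-5 values below r = 0.5 and more above it, so the unstated choice can move power either way. ANCOVA has more power than both at each r in the table.

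**Non-normal outcomes.** Simulated power (20,000 trials per setting, or 8,000 where marked *), with the 0.5 SD effect and r set on an underlying normal scale. Each cell gives r = 0.3/0.5/0.7.

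| Outcome | Kruskal-Wallis, week 5 | Linear ANCOVA | ANCOVA on ranks |
|---|---|---|---|
| Bounded, rounded 0–10 scale (mean 4, SD 2.5)* | 58/57/58% | 63/70/85% | 61/68/82% |
| Skewness about 1.75* | 58/57/58% | 58/64/80% | 61/68/83% |
| 30% at a ceiling* | 52/53/53% | 53/60/75% | 55/62/75% |
| 50% of baseline at a ceiling | 47/47/47% | 45/49/61% | 49/53/63% |
| 70% of baseline at a ceiling | 37/36/37% | 31/34/41% | 37/40/46% |
| Lognormal | 58/58/57% | 44/49/61% | 61/69/83% |

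ANCOVA on ranks matched or beat the planned rank test in every row. Linear ANCOVA matched or beat the planned rank test in the first three rows. It fell below it at low or moderate r only with heavy ceilings or lognormal data.

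**The case against.** **Baseline may well be measured.** The text is silent; it does not exclude a baseline. Section 6 describes the goniometer and tape-measure tests without attaching a time. This stands. A reader might infer that outcomes are deliberately taken at week 5 alone and that baseline will go unused, but the documents do not say so. If baseline is taken at enrolment, the section 5 point is only a documentation gap. The silence in section 7 on what is compared remains.

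**The planned comparison is legitimate.** A reader might infer that leaving out baseline biases the result. It does not: under randomization the week-5 comparison is unbiased and answers the between-group objective. Choosing ANCOVA is a recommendation on efficiency.

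**The size of the gain is assumed.** This also stands. Effect size, correlation, allocation and dropout are not given, and no primary outcome is named to attach a power figure to. At r = 0.3 the gain is small.

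**Linear ANCOVA is wrong for skewed scales.** This is true only at the extreme. The large shortfall of linear ANCOVA against ranks, 16 to 22 points, belongs to the lognormal case, which has no upper limit, whereas VAS, the questionnaires and the Berg scale have fixed limits. A reader might conclude that every bounded or doubtful outcome should go to ranks. The bounded-scale row does not support that, and such a rule would take most listed outcomes away from an effect estimate in scale units.

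**Conclusion.** The point holds as a loss of precision and clarity, worth correcting but not a threat to validity, provided that randomization is carried out as the title says. The plan states no baseline assessment and does not define the quantity compared.

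Under the assumptions listed, baseline adjustment raises power from 60% to between 63% and 87% as r goes from 0.3 to 0.7, and costs under one point if baseline carries no information. The amount depends on a correlation that the documents do not give.

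Ranks are justified for outcomes expected to be strongly skewed or to have many values at a floor or ceiling. The Berg Balance Scale is a possible case because section 5 excludes "patients with vestibular and orthopedic pathologies affecting balance". That is an inference; the documents give no Berg data.

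**What to change.** **Section 5, add:** All listed outcomes are measured in both groups before randomization and again at the end of week 5.

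**Section 7, replace the between-group rule for continuous outcomes with:** Each continuous outcome is compared between groups at week 5 by ANCOVA adjusting for its own baseline value, reporting the adjusted mean difference with 95% CI. For outcomes named in advance as expected to be strongly skewed or to have many values at a floor or ceiling (possibly the Berg Balance Scale), the test is ANCOVA on ranks in place of the unadjusted Kruskal-Wallis test, with the ANCOVA-adjusted mean difference and CI reported alongside.

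Being a bounded scale is not by itself a reason to use ranks.

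**Cost.** One set of questionnaires and goniometer, tape-measure and balance tests per patient before treatment, if not already taken at enrolment, and one degree of freedom per analysis. No new instrument is needed. Both analyses run in the SPSS package already named: for the rank version, rank the week-5 and baseline values and fit the same model.
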